## 5. Inclusion/Exclusion Criteria

Key inclusion criteria are: undergoing clinically indicated PCI; >18 years of age; able for PO medications and to provide informed consent. Key exclusion criteria: pregnant; any **DAPT(clopidogrel, prasugrel, ticagrelor) within 14 days of enrollment;** known coagulation disorders; active treatment with oral anticoagulant or low molecular weight heparin; impaired renal or hepatic function; platelets  $< 100 \times 10^3 / \text{mcl}$ ; planned use of GP2b3a for PCI; Prior TAVR or planned TAVR post PCI; and contraindications to ticagrelor or opiates.

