### 1. Abstract

With potent analgesic properties, perceived hemodynamic benefits and limited alternatives, opiates are the analgesic mainstay for acute coronary syndrome (ACS) patients reporting peri-procedural pain or nitrate-resistant chest pain. However, large observational studies suggest that opiate administration during ACS may result in adverse cardiovascular outcomes. Complimenting this, a number of recent mechanistic studies have demonstrated delayed and attenuated effects of oral dual anti-platelet therapy (DAPT) on platelet inhibition endpoints among subjects receiving intravenous morphine. These studies support the hypothesis that morphine delays the gastrointestinal absorption of DAPT medications. However, no data exist on the impact of intravenous fentanyl, a systemic opioid analgesic routinely administered during percutaneous coronary intervention (PCI) procedures, on the platelet inhibition effects of DAPT. We hypothesize that, similar to morphine, fentanyl administered at the time of PCI will reduce and delay the effect of DAPT on platelet function. As such, the primary aim of this study is to test the impact of intravenous fentanyl on residual platelet reactivity by randomizing patients undergoing PCI to a strategy of peri-procedural benzodiazepine plus non-systemic local analgesia or to the current standard of benzodiazepine plus intravenous fentanyl. Our study will address a major gap in knowledge. PCI analgesia with fentanyl is often administered concurrently with loading doses of DAPT, particularly in ACS. Given the critical need for rapid and robust inhibition of platelet function during PCI, our research study has true potential to change clinical practice, particularly if we demonstrate reduced DAPT absorption and elevated residual platelet reactivity among patients receiving fentanyl during PCI. As such, this research could result in a paradigm shift in the analgesia management of PCI and have a profound impact on optimization of post-PCI cardiac outcomes.

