### 3. Background

[figure not shown]
Morphine has long played a central role in the management of ACS. However, a 2005 observational study suggested that patients receiving morphine for pain relief in ACS had worse outcomes. In this context, recent research demonstrates that intravenous morphine delays and inhibits the absorption of oral DAPT with resultant delay in the time to maximal platelet inhibition. Hobl *et al.* administered a loading dose of 600mg clopidogrel together with either placebo or 5mg morphine intravenously in a randomized, double-blind, cross-over mechanistic trial. Morphine injection delayed clopidogrel absorption ( $T_{max}$ : 105 vs. 83 min,  $p = 0.025$ ) and reduced the total exposure to its active metabolite by 34% ( $p = 0.001$ , **figure 1**). Morphine also resulted in higher residual platelet aggregation and delayed maximal inhibition of platelets by 2 hours ( $n = 24$ ;  $p < 0.001$ ). Similar results have recently been reported for subjects receiving ticagrelor. Morphine's association with emesis, inhibition of gastric emptying and reduced GI motility is hypothesised as the cause.

Delayed and reduced absorption of DAPT in ACS patients is likely to translate into worse cardiovascular outcomes because maximal inhibition of platelet function is necessary to treat intracoronary atherosclerotic plaque rupture and thrombosis, as well as to minimize the risk of in-stent thrombosis among patients who receive coronary stents at the time of PCI. In keeping with this, morphine has also recently been associated with suboptimal reperfusion after PCI in patients with ACS (**figure 2**). As a consequence, 2015 European guidelines now state, “*in ACS patients whose ischemic symptoms are not relieved by nitrates and beta-blockers, opiate administration is reasonable..., with the caveat that morphine may slow intestinal absorption of oral platelet inhibitors.*”

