## 7. Study Statistics

### a. Primary outcome variable.

In both randomized groups P2Y12 reactivity units (PRUs), measured using VerifyNow, will be determined at 0, 0.5, 1, 2, 4, and 24 hours. The primary outcome will be mean PRU at 2 hours.

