### b. Secondary outcome variables.

Additional secondary platelet outcomes will include light transmission aggregometry (LTA) at 2 hours, and also time-averaged PRU using mixed effects models. Given we hypothesize fentanyl may impair platelet inhibition due to reduced gastrointestinal absorption of ticagrelor, we will also compare ticagrelor pharmacokinetics in both arms, as determined by the area under the curve of active metabolite by liquid chromatography mass spectrometry (at 0, 0.5, 1, 2, 4 and 24 hours). We will also determine the impact of fentanyl on myocardial injury, as measured by high-sensitivity Troponin-I in the serum. In all 300 patients consented, we will also compare patient reported pain among both groups using the visual analog scale and the numeric rating scale (NRS). (12) These simple to perform subjective assessments can measure clinically meaningful differences in pain (e.g. a difference of 30% on the NRS). (12)

|   | YES                      | NO                       | Collection Date and TIME          |
|---|--------------------------|--------------------------|-----------------------------------|
| Pre Procedure Blood – Hour 0
• Platelet Function
- Verify Now  |  |  |    /    /    |
| Intra Procedure Blood- Hour 0.5
• Pharmacokinetics
• Platelet Function
- Verify Now   |  |  |    /    /    |
| Intra Procedure Blood- Hour 1
• Pharmacokinetics
• Platelet Function
- Verify Now   |  |  |    /    /    |
| Post Procedure Blood – Hour 2
• Pharmacokinetics
• Platelet Function
- Verify Now
- ADP-based LTA
• High Sensitivity Troponin
• Pain by Self-Report (visual scale) |  |  |    /    /    |
| Post Procedure Blood – Hour 4
• Pharmacokinetics
• Platelet Function
- Verify Now
• High Sensitivity Troponin  |  |  |    /    /    |
| Post Procedure Blood – Hour 24
• Pharmacokinetics
• Platelet Function
- Verify Now  |  |  |    /    /    |

*c. Statistical plan including sample size justification and interim data analysis.*

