Based on prior data , we anticipate a 2 hour PRU of ~230 (Standard Deviation of 25) among patients receiving 180 mg ticagrelor without opiate and estimate a conservative effect size of 20% increase in 2hr PRU among those who receive fentanyl . These calculations yield a sample size estimate of  $\leq 23$  subjects per group (approx. 50 total) to achieve 90% power (2 sided alpha 0.05). Accounting for drop out and unanticipated increases in 2hr PRU variability, and to provide power for subgroup analyses, we will accrue 70 patients who undergo DAPT loading in total. In all analyses a value of  $p < 0.05$  will be considered statistically significant.

*d. Early stopping rules.*

N/A

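### Should the plan exclude, or adjust for, opiates given before randomisation?

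*Combined protocol and SAP*

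**What the plan says.** Section 5 of the combined protocol and SAP guards the platelet endpoint against other drugs. It excludes "DAPT(clopidogrel, prasugrel, ticagrelor) within 14 days of enrollment", active oral anticoagulant or low molecular weight heparin treatment, and planned GP2b3a use. Its only opiate item comes at the end of the list: "planned use of GP2b3a for PCI; Prior TAVR or planned TAVR post PCI; and contraindications to ticagrelor or opiates". That removes patients who cannot take an opiate, not patients who have just had one. The list is introduced as the key criteria, so it may not be complete.

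Section 7a fixes the endpoint: "The primary outcome will be mean PRU at 2 hours". Section 7b adds aggregometry at 2 hours, "also time-averaged PRU using mixed effects models", ticagrelor pharmacokinetics, troponin and pain. No covariate is named for any of these. Section 7c takes its control value, a PRU of about 230 with SD 25, from prior data "among patients receiving 180 mg ticagrelor without opiate". It raises the total to 70, partly "to provide power for subgroup analyses", and does not name the subgroups. Section 4g specifies analysis by initial randomised allocation.

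**The concern.** The protocol's own argument makes a prior opiate look relevant. Section 3 states that "recent research demonstrates that intravenous morphine delays and inhibits the absorption of oral DAPT", and Section 6a treats the trial's fentanyl dose as equipotent with the morphine dose of two cited trials. The Abstract says that "opiates are the analgesic mainstay for acute coronary syndrome (ACS) patients reporting peri-procedural pain or nitrate-resistant chest pain", and Section 5 admits any clinically indicated PCI, so ACS patients can enter. Some controls could therefore reach the catheterisation laboratory with the exposure that the trial means to withhold from them.

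The hour-0 PRU would not reveal this. It is a pre-procedure sample, taken before any ticagrelor has been loaded, and the suspected effect is on later absorption.

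At stake is a difference smaller than the one planned. A reader who saw a modest difference could not tell a weak fentanyl effect from a control group that was partly exposed.

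**Working it through.** **Inputs from Section 7c.** Control mean 230, SD 25, effect 20%, two-sided alpha 0.05, 90% power, at most 23 per group, 70 accrued (35 per arm at 1:1).

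**The plan's own figure.** Planned difference = 0.20 × 230 = 46 PRU. A two-sample t-test with SD 25 and 90% power needs 7.3, so 8 per group, not 23. The SD that makes 23 per group correct for 46 PRU is about 47. The stated upper limit of 23 is not contradicted, but the stated inputs do not produce it. This matters here only because it suggests trying a larger SD as well.

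**Assumptions (not in the documents).** Let p be the share of patients given an opiate before randomisation, equal in both arms in expectation. Let r be the fraction of the fentanyl effect that the prior opiate already exerts in controls. Assume it adds nothing in patients who then receive fentanyl. Then:

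expected difference = 46 × (1 − p × r)

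The control variance rises to SD² + p(1 − p)(46r)².

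| p | r = 0 | r = 0.5 | r = 1 |
|---|---|---|---|
| 5% | 46 | 44.9 | 43.7 |
| 10% | 46 | 43.7 | 41.4 |
| 20% | 46 | 41.4 | 36.8 |

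If the prior opiate raises PRU equally in both arms, so that the effects add, the difference stays at 46 and only the variance grows.

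**Power at 35 per arm, SD 25.** The worst cell is p = 20%, r = 1:
- control SD = √(625 + 0.2 × 0.8 × 46²) = 31.0
- standard error = √((963.6 + 625)/35) = 6.74
- difference 36.8, power above 99.9%

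Every other cell is better. Under the full-effect assumption (r = 1), power falls below 90% only when about half of all patients had a prior opiate.

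**Power at 35 per arm, SD 47.** Power is 98% with no dilution. At p = 20% it is about 95% for r = 0.5. For r = 1 it is 87.5% with the widened control variance, or 90% without it.

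**What an added analysis would return (SD 25, p = 20%, r = 0.5).**
- Intention to treat: 41 ± 12.3 PRU.
- With prior opiate as a covariate: ± 12.1, a gain of 0.2 PRU in half-width.
- Opiate-naive patients only (0.8 × 35 = 28 per arm): about 46 ± 13.3.
- Opiate-naive minus overall, by simulation: 4.6 on average, 95% range −1.7 to 11.5. At p = 10% it is 2.3, range −1.9 to 7.5. At p = 20% and r = 1 it is 9.2, range 1.3 to 18.7.

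At p = 10% the covariate would rest on 0.1 × 35 = 3.5 exposed patients per arm.

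**The case for a change.** The strongest case for acting is that the remedy looks almost free: one data field, one covariate and one supplementary comparison defined by a baseline variable, with the primary analysis and eligibility left alone. A definition of prior exposure fixed in advance is also better than one chosen after the results are known. The 23 per group hints that the SD may really be nearer 47, where 20% exposure at full effect brings power to 87.5–90%. By their titles, the two cited morphine–ticagrelor trials disagree on antiplatelet action, but both report lower ticagrelor exposure or concentrations, and ticagrelor pharmacokinetics is a secondary objective.

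The textual gap stands, and so does the preference for deciding such things early. The rest is weaker.

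- **Exposure may be small.** ACS is not required for entry. The P2Y12 and heparin exclusions may remove some pre-treated ACS patients. The Abstract's remark also covers pain around the procedure, and analgesia at that point is what the trial randomises.
- **The SD of 47 is not in the plan.** It is solved back from a sample size that the stated inputs do not give.
- **The remedy would not deliver a control group without opiates.** Sections 4d, 4f and 8a allow bail-out opiates after randomisation, so patients who are opiate-naive at baseline need not remain so.
- **The field costs more than it seems.** Patients are randomised before it is known whether they need a stent. The field would have to be completed in every randomised patient, possibly about 300, to serve the roughly 70 who are loaded with ticagrelor.

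**Conclusion.** The observation is accurate, but the plan as written still gives a sound answer to the question in Section 2, which concerns randomisation to fentanyl. Prior opiate use is a baseline characteristic that randomisation balances on average. It does not bias the comparison, and at the stated SD it does not cost meaningful power. The reference to controls without an opiate in Section 7c describes where a planning mean came from; it is not an enrolment condition.

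Any dilution needs three things that the documents do not supply: an appreciable exposure share, a real effect of the earlier opiate on PRU at 2 hours, and an effect that does not add to that of fentanyl. With 5–10% exposed, the loss is 1.1 to 4.6 PRU, against an interval of about ± 12. With 20% exposed it reaches 4.6 to 9.2 PRU, and only the full-effect end of that range would usually show up in an opiate-naive comparison. Reduced power would need an SD near 47 as well.

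Analysts who hold medication records can describe prior opiate use alongside the other baseline characteristics and note it when discussing the size of the effect. A formal added analysis would be a matter of preference with little gain, so no change to the plan follows.

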## 6. Drugs/ Substances/ Devices

a. *The rationale for choosing the drug and dose or for choosing the device to be used.*

Subjects randomized to the current standard of peri-procedural intravenous benzodiazepine plus intravenous fentanyl will receive an initial dose of 1 mg of midazolam and 25-50 mcg of fentanyl. Subsequent doses of either medicine can be provided as necessary. The rationale for this dosing schedule is that it is the standard of care. Furthermore, 25-50mcg of fentanyl is equipotent with the morphine dose used by Hobl and Kubica in two recent trials (5mg).  Subjects randomized to the research strategy of peri-procedural intravenous benzodiazepine plus non-systemic analgesia will receive an initial dose of 1 mg of midazolam (with titrations allowed as necessary) and local anaesthetic (e.g. subcutaneous lidocaine). The rationale for this strategy is to maintain comfort during the case without exposing the subjects to opiates.

b. *Justification and safety information if FDA approved drugs will be administered for non-FDA approved indications or if doses or routes of administration or participant populations are changed.*

N/A

*c. Justification and safety information if non-FDA approved drugs without an IND will be administered.*

N/A

Date: 7/20/16  
Principal Investigator: [name]  
Application Number: IRB00089755

## 7. Study Statistics

### a. Primary outcome variable.

In both randomized groups P2Y12 reactivity units (PRUs), measured using VerifyNow, will be determined at 0, 0.5, 1, 2, 4, and 24 hours. The primary outcome will be mean PRU at 2 hours.

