### 2. Objectives

**Primary Objective:** We will test the hypothesis that randomization to fentanyl will be associated with higher residual platelet reactivity, as determined by mean P2Y12 reactivity units (PRUs) at 2 hours, among persons undergoing PCI with IV fentanyl analgesia (as well as aspirin and ticagrelor), compared to subjects randomized to undergo PCI with non-systemic analgesia.

**Secondary Objective:** To test the hypothesis that fentanyl administered during PCI will adversely impact the pharmacokinetics of ticagrelor, as determined by the area under the curve of active metabolite measured using liquid chromatography tandem mass spectrometry.

[figure not shown]
**Secondary Objective:** To test for differences in patient reported pain scores and biomarkers of myocardial injury, comparing PCI patients randomized to peri-procedural benzodiazepine plus non-systemic local analgesia or to the current standard of benzodiazepine plus intravenous fentanyl.

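### Hour-0 PRU is measured in both arms but has no stated role in the 2-hour comparison; adjusting for it is a likely, not certain, gain in precision that needs no new sample

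*Combined protocol and SAP*

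**What the plan says.** The primary objective in section 2 compares the arms "as determined by mean P2Y12 reactivity units (PRUs) at 2 hours", and section 7a repeats it: "The primary outcome will be mean PRU at 2 hours". On the measurement schedule, section 7a says: "In both randomized groups P2Y12 reactivity units (PRUs), measured using VerifyNow, will be determined at 0, 0.5, 1, 2, 4, and 24 hours". The collection table in section 7b heads the first sample "Pre Procedure Blood – Hour 0". Section 5 excludes patients exposed to "DAPT(clopidogrel, prasugrel, ticagrelor) within 14 days of enrollment", so hour-0 PRU should be free of P2Y12 inhibitors.

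Section 7c gives a sample size and a significance threshold. It names no test, model or covariate for the primary comparison. The one longitudinal analysis, in section 7b, is "time-averaged PRU using mixed effects models"; the plan does not say whether hour 0 is a response, a covariate or left out. Nothing in the document mentions baseline adjustment or change from baseline.

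Section 4a counts all sampling times, including 0, from randomisation, whereas the collection table ties hour 0 to the procedure.

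**The concern.** A pre-treatment value of the endpoint, on the same assay and in both arms, is the obvious covariate in a trial of 70 patients. If it predicts the 2-hour value, adjustment removes part of the between-patient variance at no cost in samples. If the plan is silent, the choice may be made after the data are seen, in a trial where patients and treating staff know the allocation.

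The secondary mixed model raises a further question, about what is estimated. Hour 0 is on the list of PRU times. If it entered the time average as an outcome, the average would include a time at which study treatment cannot yet have acted, and the estimated effect would shrink.

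**Working it through.** **Inputs.** From section 7c: control mean 230 PRU, SD 25, increase of 20%, so the difference is 0.20 × 230 = 46 PRU; two-sided alpha 0.05; 90% power; 70 patients. Section 4a gives 1:1 allocation, so 35 per arm is taken. Assumed: r, the within-arm correlation of hour-0 and 2-hour PRU, shown from 0 to 0.5.

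**The plan's own figure.** n per arm = 2(1.960 + 1.282)² × 25² / 46² = 6.2, so 7 by the normal approximation and 8 by the t distribution. The plan states at most 23 per group, about 50 in total. The figure of about 50 does not follow from the stated inputs. That is a separate matter, but it means that power on the plan's own inputs is not in doubt: with 35 per arm it exceeds 99.9%, adjusted or not.

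**Unadjusted precision.** SE = 25 × √(2/35) = 5.98. With 68 df, t = 1.9955, so the 95% half-width is 11.93 PRU. By the noncentral t, the difference detectable with 90% power is 19.65 PRU.

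**Adjusted precision.** Adjustment multiplies the variance by (1 − r²). Estimating one slope multiplies it by about 1 + 1/(N − 4) = 1 + 1/66 = 1.015. With 67 df, t = 1.9960.

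| r | variance factor | SE | 95% half-width | detectable at 90% power |
|---|---|---|---|---|
| unadjusted | 1 | 5.98 | 11.93 | 19.65 |
| 0 | 1.015 | 6.02 | 12.02 | 19.80 |
| 0.1 | 1.005 | 5.99 | 11.96 | 19.70 |
| 0.2 | 0.975 | 5.90 | 11.78 | 19.40 |
| 0.3 | 0.924 | 5.74 | 11.47 | 18.89 |
| 0.5 | 0.761 | 5.22 | 10.41 | 17.15 |

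Break-even: (1 − r²) × 67/66 = 1 gives r² = 1/67, so r = 0.12.

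**If variability is larger.** Section 7c sets its margin by "Accounting for drop out and unanticipated increases in 2hr PRU variability". An SD of about 47 is what 23 per group, 90% power and 46 PRU would imply; it is a back-calculation, not a planned value. With the same formulas:

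- 35 per arm: power is 98.1% unadjusted, and 97.9%, 98.7% and 99.6% adjusted at r = 0, 0.3 and 0.5.
- 25 per arm (slope factor 1 + 1/46 = 1.022): power is 92.3% unadjusted, and 93.9% and 97.2% adjusted at r = 0.3 and 0.5.

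**Mixed model.** Suppose hour 0 were one of the averaged outcomes, with zero effect there. With six equally weighted times the effect is diluted by 1/6, or 17%. With trapezoidal time weights over 0 to 24 hours, hour 0 carries (0.5/2)/24 = 0.0104, or about 1%.

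**The case against.** The strongest objection is that r may be low. Hour 0 is off drug and 2 hours is on drug. Section 4a counts time from randomisation, but ticagrelor is given only if a stent proves necessary, so 2 hours is a variable interval after the load; hour-0 PRU cannot explain that source of spread. At r of 0.1 or less the gain is nil or slightly negative, and at 0.3 it is about half a PRU in half-width. This stands: the gain cannot be promised. What favours adjusting is the asymmetry, a loss of about 1.5% of variance at worst against a reduction of about 24% at r = 0.5.

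It is also fair to say that the broader gap is the absence of any named primary model. Adjustment is a recommendation about how to fill that gap, not the correction of an error.

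The hour-0 timing is a condition on the advice. The two descriptions are compatible if blood is drawn after randomisation but before the procedure. The plan does not state that the draw comes before study analgesia and the ticagrelor load, and the covariate is a true baseline only if it does.

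A reader might infer three stronger things that the documents do not support:

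- That the unadjusted comparison is biased or underpowered. Randomisation makes it valid, and power on the stated inputs is above 99.9%.
- That the plan prescribes an unadjusted test. It prescribes none.
- That the mixed model will average hour 0 in and dilute the effect. The plan is silent, and the dilution is conditional on that choice.

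**Conclusion.** The omission is real: a same-assay, pre-procedure PRU is collected in both arms and has no stated use in the primary comparison. Specifying it as a covariate is a worthwhile, nearly free improvement whose benefit is likely but not assured. On the planned SD of 25 and 35 per arm, it changes the 95% half-width from 11.9 PRU to between 12.0 (r = 0) and 10.4 (r = 0.5), with a net gain once r exceeds about 0.12. It does not alter the power conclusion on the plan's own inputs. Its practical value is a tighter estimate and some reserve if variability or dropout is worse than planned.

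This rests on an assumed range for r, a common SD, equal arms, a linear relation, and an hour-0 sample drawn before any study treatment. The mixed-model point concerns a secondary outcome only: how hour 0 is handled could move the estimated effect by about 1% to 17%, so it should be fixed in advance.

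**What to change.** In section 7:

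- State the primary analysis as a linear model of 2-hour PRU on randomised arm with hour-0 PRU as covariate. Report the adjusted difference with its 95% CI, and give the unadjusted difference as a sensitivity analysis.
- Fill a missing hour-0 value with the overall mean of both arms, so that no patient is lost from the model for want of a baseline.
- State that the hour-0 sample is drawn before study analgesia and the ticagrelor load, and reconcile section 4a with the collection table in section 7b.
- For the mixed model, define the time-averaged effect over post-baseline times only and state the time weights. Either enter hour-0 PRU as a covariate, or keep it in the response with baseline means constrained equal between arms.

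The cost is a few sentences and one degree of freedom. No sample, visit or assay is added.
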